3.5 Safety endpoints

The safety analysis will include all patients screened and enrolled for whom has been given at least one dose by subcutaneous (s.c.) injection of VAL201.

The number and percent of subjects experiencing Adverse Events (AEs) will be reported by dose. In addition the incidence of AE and suspected DLTs will be graded according to the Common Terminology Criteria for AEs (CTCAE), version 4.03.

In order to assess the primary objective of the analysis the following classification of the safety variables will be apply:

Forms				
Title		Statistical Analysis Plan Template		
Code		Version	Effective Date	Page
FRM_ST03_032		01	23 Apr 2015	12 of 24

Dose Limiting Toxicity (DLT)

A DLT is defined as a drug –related Grade 3 or 4 AE (from CTCAE version 4.03) that, in the opinion of the Investigator and/or CRC, represents a clinically significant hazard to the patient; a list of exceptions is presented in Section 4.2.1 of the study protocol.

DLT events will also be considered in terms of:

- inability to administer the planned Cycle 1 dose administration schedule;
- clinically significant toxicity events considered related to VAL201 which lead to a dose delay of more than 7 days during Cycle 1.

Pre-treatment adverse events-

An AE will be classified as pre-treatment AE if it starts before the date/time of day of first medication intake in the study.

Treatment-emergent adverse event (TEAE)

An AE will be classified as a TEAE if it starts on or after the date/time of day 1 cycle 1 of the study. In case of missing or incomplete dates/times not allowing a direct allocation to any of the two categories of AEs, it will be considered to be treatment-emergent, unless the stop date is known to be prior to the first administration of the study medication. The AE will be allocated to the first category allowed by the available data, according to the following order:

- TEAE
- Pre-treatment.

Serious adverse event (SAE)

A SAE is an AE judged as serious.

Adverse Event Related to study drug

An AE is considered as related to study drug if it is judged as “Possibly Related”, “Probably Related” or “Definitely Related” or with missing relationship.

Adverse event leading to death

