4.4 Handling of missing and incomplete data

Missing values will be included in the denominator count when computing percentages. Only the non-missing values will be evaluated for computing summary statistics. AEs that have missing onset dates will be considered to be treatment-emergent, unless the stop date is known to be prior to the first administration of VAL201.

In order to calculate the duration of tumor, the following rules will be applied for partial dates of histological/cytological diagnosis:

- if only the day is missing, the 15th of the month will be assumed;
- if the day and the month are missing, 30th June will be assumed.

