6.1 Analysis of primary objective

The primary objective of this study is to estimate the MTD/MAD of VAL201 throughout an accelerated dose escalation design (3+3 patients per dose level). The first 2 cohorts will enroll 1 patient only (see Section 1.5 of the study protocol). For each cohort, patients will be followed up for adverse events (AEs) and DLT during each cycle.

The escalating dose will be determined if 0 patients out of 3 or 1 patient out of 6 experience a DLT, and de-escalating if 2 or more patients with DLTs are encountered. Therefore the MTD will be the highest dose level at which 0 of 3 or 1 of 6 patients experience a DLT.

The CRC will review all patient safety data at the end of Cycle 1 and only permit dose escalation to the next dose level where there are no safety concerns. Where the CRC suspects that drug-related events have occurred that merit further exploration at that dose level, they will request that Cohort 1 or 2 must enroll 3 more patients in order to more thoroughly evaluate safety events prior to escalation. Cohorts of 3 patients will be enrolled from the 3rd cohort onwards (or earlier where the CRC recommend due to safety data evaluation) thereafter the cohort will be expanded to 6 patients upon identification of a DLT. If a second DLT is reported this will be declared the MTD.

There will be no formal statistical analysis in the dose-escalation phase. However, safety data such as AEs and DLT will be listed and summarised by dose level separately using descriptive statistics. Pre-treatment AEs will be listed.

Forms				
Title		Statistical Analysis Plan Template		
Code		Version	Effective Date	Page
FRM_ST03_032		01	23 Apr 2015	20 of 24

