6.2.1 Assessment of the safety and tolerability

The assessment of safety and tolerability will be based on the safety data set; the evaluation of AEs will be carried throughout every cycle including follow up period, which is defined as final study visit performed 30 +/- 5 days after last dose of VAL201.

Frequencies and percentages of patients experiencing one or more AEs will be summarized and listed by:

- Dose level where applicable.
- Relationship to the study drug.
- Severity.

Severe Adverse Events (SAEs) and DLTs will be presented separately.

The number of AEs leading to death and treatment emergent AE (TEAE) will be summarised by descriptive statistics. AEs will be coded using the MedDRA dictionary (version 17.0). The SOCs and PTs will be used for tabulation. The number and the percentage of patients with at least one AE will be presented by SOC and PT.

Safety parameters such as vital signs will be listed and summarized as described in section 5.10 of this SAP. Laboratory parameters such as haematology, coagulation, clinical chemistry and urinalysis data will be listed and summarised as indicated in section 5.11 of this SAP. Physical examination and ECG parameters will be listed as indicated in section 5.8 and 5.10 respectively of this SAP.

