7.2 Tables listings and figures

7.2.1 Tables:

 cros nt	Forms			
	Title	Statistical Analysis Plan Template		
	Code	Version	Effective Date	Page
	FRM_ST03_032	01	23 Apr 2015	22 of 24

TABLE 14.1-1	DISPOSITION OF PATIENTS / SUMMARY OF ALL PATIENTS AND ANALYSIS SET
TABLE 14.1-2.1	SUMMARY OF MAJOR PROTOCOL DEVIATION / INTENT TO TREAT POPULATION
TABLE 14.1-2.2	SUMMARY OF MINOR PROTOCOL DEVIATION / INTENT TO TREAT POPULATION
TABLE 14.1-3.1	DEMOGRAPHIC CHARACTERISTIC / INTENT TO TREAT POPULATION
TABLE 14.1-4	SUMMARY OF TUMOUR ASSESSMENT / INTENT TO TREAT POPULATION
TABLE 14.1-5.1	MEDICAL HISTORY BY SYSTEM ORGAN CLASS AND PREFERRED TERM / INTENT TO TREAT POPULATION
TABLE 14.1-5.2	CONCOMITANT DISEASE BY SYSTEM ORGAN CLASS AND PREFERRED TERM / INTENT TO TREAT POPULATION
TABLE 14.1-6.1	PREVIOUS MEDICATIONS / INTENT TO TREAT POPULATION
TABLE 14.1-6.2	CONCOMITANT MEDICATIONS / INTENT TO TREAT POPULATION
TABLE 14.2-1	SUMMARY OF DOSE LIMITING TOXICITY (DLT) BY COHORT / SAFETY POPULATION
TABLE 14.2-3.1	PROSTATE SPECIFIC ANTIGEN (PSA) ASSESSMENT / INTENT TO TREAT POPULATION
TABLE 14.2-3.2	PROSTATE SPECIFIC ANTIGEN (PSA) ASSESSMENT / PER PROTOCOL POPULATION
TABLE T14.2-4.1	SUMMARY OF RESPONSE RATE ANTI TUMOUR ACTIVITY / INENT TO TREAT POPULATION
TABLE T14.2-4.2	SUMMARY OF RESPONSE RATE ANTI TUMOUR ACTIVITY / PER PROTOCOL POPULATION
TABLE T14.3.1-1.1	SUMMARY OF TREATMENT-EMERGENT ADVERSE EVENTS BY DOSE/ DOSE ESCALATION SAFETY POPULATION
TABLE T14.3.1-2.1	SUMMARY OF TREATMENT EMERGENT ADVERSE EVENT BY SYSTEM ORGAN CLASS AND BY DOSE / DOSE ESCALATION SAFETY POPULATION
TABLE T14.3.1-3.1	SUMMARY OF TREATMENT EMERGENT ADVERSE EVENT BY SYSTEM ORGAN CLASS AND BY SEVERITY / DOSE ESCALATION SAFETY POPULATION
TABLE T14.3.1-4.1	SUMMARY OF TREATMENT EMERGENT ADVERSE EVENT BY SYSTEM ORGAN CLASS AND BY CAUSALITY / DOSE ESCALATION SAFETY POPULATION
TABLE 14.3.4-1.1	ESTERN CO-OPERATIVE ONCOLOGY GROUP (ECOG) PERFORMANCE STATUS / INTENT TO TREAT POPULATION
TABLE 14.3.4-1.2	ESTERN CO-OPERATIVE ONCOLOGY GROUP (ECOG) PERFORMANCE STATUS / PER PROTOCOL POPULATION
TABLE 14.3.4-2.1	SUMMARY VITAL SIGNS BY CYCLE AND VISIT / INTENT TO TREAT POPULATION

 cros nt	Forms			
	Title	Statistical Analysis Plan Template		
	Code	Version	Effective Date	Page
	FRM_ST03_032	01	23 Apr 2015	23 of 24

TABLE 14.3.4-2.2	SUMMARY VITAL SIGNS BY CYCLE AND VISIT / PER PROTOCOL POPULATION
TABLE 14.3.4-3.1.1	LABORATORY PARAMETERS: CLINICAL CHEMISTRY BY CYCLE AND TIME POINTS / INTENT TO TREAT POPULATION

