TABLE 14.3.4-3.1.2	LABORATORY PARAMETERS: HAEMATOLOGY AND COAGULATION BY CYCLE AND TIME POINTS / INTENT TO TREAT POPULATION
TABLE 14.3.4-3.1.3	LABORATORY PARAMETERS: URINALYSIS BY CYCLE AND TIME POINTS / INTENT TO TREAT POPULATION
TABLE 14.3.4-3.2.1	LABORATORY PARAMETERS: CLINICAL CHEMISTRY BY CYCLE AND TIME POINTS / PER PROTOCOL POPULATION
TABLE 14.3.4-3.2.2	LABORATORY PARAMETERS: HAEMATOLOGY AND COAGULATION BY CYCLE AND TIME POINTS / PER PROTOCOL POPULATION
TABLE 14.3.4-3.2.3	LABORATORY PARAMETERS: URINALYSIS BY CYCLE AND TIME POINTS / PER PROTOCOL POPULATION

7.2.2 Listings:

LISTING 16.2.1-1	DISPOSITION OF PATIENTS / ALL PATIENTS
LISTING 16.2.2-1	PROTOCOL DEVIATIONS / INTENT TO TREAT POPULATION
LISTING 16.2.3-1	DEMOGRAPHIC AND BASELINE CHARACTERISTICS / INTENT TO TREAT POPULATION
LISTING 16.2.4-1	PHYSICAL EXAMINATIONS / INTENT TO TREAT POPULATION
LISTING 16.2.4-2	PAST-CONCOMITANT DISEASES / INTENT TO TREAT POPULATION
LISTING 16.2.4-3	STUDY CANCER HISTORY / INTENT TO TREAT POPULATION
LISTING 16.2.4-4	TUMOUR ASSESSMENT / INTENT TO TREAT POPULATION
LISTING 16.2.5-1	MEDICATIONS / INTENT TO TREAT POPULATION
LISTING 16.2.6-1	PROSTATE SPECIFIC ANTIGEN (PSA) / INTENT TO TREAT POPULATION
LISTING 16.2.6-2	OTHER SOLID TUMOUR / INTENT TO TREAT POPULATION
LISTING 16.2.7-1	PRE-TREATMENT ADVERSE EVENTS / INTENT TO TREAT POPULATION
LISTING 16.2.7-2.1	TREATMENT-EMERGENT ADVERSE EVENTS / SAFETY POPULATION
LISTING 16.2.7-2.2	SERIOUS TREATMENT-EMERGENT ADVERSE EVENTS / SAFETY POPULATION
LISTING 16.2.7-2.3	TREATMENT-EMERGENT ADVERSE DRUG REACTIONS / SAFETY POPULATION
LISTING 16.2.7-2.4	TREATMENT-EMERGENT ADVERSE EVENTS LEADING TO DISCONTINUATION / SAFETY POPULATION
LISTING 16.2.7-2.5	TREATMENT-EMERGENT ADVERSE EVENTS AS CODED / SAFETY POPULATION

Forms				
Title		Statistical Analysis Plan Template		
Code		Version	Effective Date	Page
FRM_ST03_032		01	23 Apr 2015	24 of 24

LISTING 16.2.8-1	VITAL SIGNS / INTENT TO TREAT POPULATION
LISTING 16.2.8-2	12-LEAD ECG / INTENT TO TREAT POPULATION
LISTING 16.2.8-3	ESTERN CO-OPERATIVE ONCOLOGY GROUP (ECOG) PERFORMANCE STATUS / INTENT TO TREAT POPULATION
LISTING 16.2.8-4.1	LABORATORY PARAMETERS: CLINICAL CHEMISTRY / INTENT TO TREAT POPULATION
LISTING 16.2.8-4.2	LABORATORY PARAMETERS: HEAMATOLOGY AND COAGULATION / INTENT TO TREAT POPULATION
LISTING 16.2.8-4.3	LABORATORY PARAMETERS: URINALYSIS / INTENT TO TREAT POPULATION
LISTING 16.2.8-6	PK PARAMETERS / PK POPULATION

7.2.3 Figures:

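### The TEAE definition has no worsening criterion, so an AE that starts before the first dose and worsens on VAL201 is missing from all four TEAE tables unless it is recorded as a new AE

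*SAP*

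**What the plan says.** SAP 3.5 sorts adverse events into two classes.

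- Treatment-emergent: "An AE will be classified as a TEAE if it starts on or after the date/time of day 1 cycle 1 of the study".
- Pre-treatment: "An AE will be classified as pre-treatment AE if it starts before the date/time of day of first medication intake in the study".

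The rule for missing dates in SAP 4.4 also works on dates only: "AEs that have missing onset dates will be considered to be treatment-emergent", unless the stop date is known to precede the first administration.

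The outputs follow this split. For pre-treatment events SAP 6.1 says "Pre-treatment AEs will be listed", and the only output for them in SAP 7.2.2 is Listing 16.2.7-1, "PRE-TREATMENT ADVERSE EVENTS / INTENT TO TREAT POPULATION". SAP 7.2.1 has four AE tables, T14.3.1-1.1, -2.1, -3.1 and -4.1. All are restricted to treatment-emergent events; the first is titled "SUMMARY OF TREATMENT-EMERGENT ADVERSE EVENTS BY DOSE/ DOSE ESCALATION SAFETY POPULATION". The listings of serious events, drug reactions and events leading to discontinuation (16.2.7-2.2 to -2.4) carry the same restriction.

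The text of SAP 6.2.1 is wider than its tables. It says "Frequencies and percentages of patients experiencing one or more AEs will be summarized and listed by" dose level, relationship and severity, with no treatment-emergent restriction.

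**The concern.** Definitions of treatment emergence usually have two limbs: new onset after dosing, and worsening after dosing of something already present. The SAP has only the first. An event that begins at a low grade before the first dose and becomes Grade 3, serious or drug-related on VAL201 can then be left out of the tables meant to show incidence, severity and causality by dose.

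Safety and tolerability is a secondary objective, and the primary objective also rests on safety data. The planned dose groups are very small, so a single omitted patient is visible in the results. The omission also runs against the plan's own leaning: unclear dates default to treatment-emergent and a missing relationship counts as related (SAP 3.5). Both of those rules err towards counting; the worsening case errs towards leaving out. That looks like an oversight and not a choice.

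**Working it through.** The plan states no figure to reproduce. The check is to follow an event through the rules.

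**Inputs:** the two definitions and the rule for counting AEs (SAP 3.5); the missing-date rule (4.4); the concomitant disease rule (5.5); the cohort sizes (3.1); the screening window of up to 28 days (3.2); the tables and listings (7.2.1, 7.2.2).

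**Tracing four cases:**

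1. *AE starts between screening and first dose, worsens on treatment, original onset date kept.* The start precedes the first dose, so it is pre-treatment. It appears in Listing 16.2.7-1 and in none of the four T14.3.1 tables. If it becomes serious, drug-related or a cause of discontinuation, it is also absent from Listings 16.2.7-2.2 to -2.4.
2. *As case 1, but the worsening is judged a DLT.* The DLT definition in 3.5 uses relatedness, grade and clinical judgement, not the start date. Table 14.2-1, "SUMMARY OF DOSE LIMITING TOXICITY (DLT) BY COHORT / SAFETY POPULATION", is not restricted to TEAEs. The event is counted there but still missing from the four T14.3.1 tables.
3. *As case 1, but the worsening is entered as a new AE with its own onset date.* The new record starts after dosing, so it is a TEAE and is tabulated.
4. *Disease already ongoing at the screening visit that worsens on treatment.* SAP 5.5 classes it as concomitant disease, not as a pre-treatment AE. Its worsening can reach the AE data only as a new record, which then behaves as in case 3.

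The gap is therefore case 1, and the T14.3.1 part of case 2.

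**Size of one omission.** SAP 3.1 plans 1 patient in each of the first two cohorts and 3 from the third cohort onwards.

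- 1 patient: 1/1 = 100% becomes 0/1 = 0%.
- 3 patients: 1/3 = 33% becomes 0/3 = 0%.

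**Time anchors.** The TEAE class runs from Cycle 1 Day 1 and the pre-treatment class ends at first medication intake. An event that begins on Cycle 1 Day 1 before the injection can meet both definitions. The order of preference given in 3.5 (TEAE first) would settle it, but it is written for incomplete dates. This is a separate wording point that the same edit can close.

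**The case against.** The strongest reply is that recording a worsening is a matter for the protocol and the CRF instructions, which are not at hand. If these require a new AE record whenever the grade rises, the date-only rule captures the event. SAP 3.5 does foresee several records with the same preferred term and counts them separately. This stands as a limit on the finding, but it does not remove it. The counting rule says how to treat two records that exist; it does not require a second one. The SAP neither states nor cites such a convention, and a programmer following 3.5 would exclude a worsening held in one record.

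A second reply is that worsening shows up elsewhere. This is partly right. Laboratory results are summarised by investigator interpretation, including clinically significant abnormality, at each cycle (5.11), and ECOG status and vital signs are summarised by cycle (5.7, 5.9). But 5.11 specifies no CTCAE grade or shift from baseline, ECG and physical examination are only listed (5.10, 5.8), and none of these outputs replaces AE incidence by severity and causality.

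A reader might infer more than the documents support:

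- *That any condition present before dosing is affected.* Diseases ongoing at screening are concomitant diseases under 5.5, so many pre-existing symptoms of advanced cancer never become pre-treatment AEs.
- *That the event vanishes from every safety output.* It remains in Listing 16.2.7-1, and in Table 14.2-1 if judged a DLT.
- *That the MTD could be set wrongly.* The MTD rule uses DLT counts, which do not depend on the TEAE class, and the Cohort Review Committee reviews all patient safety data (6.1).
- *That incidence is understated at every dose.* That would need such a case at each dose level.

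**Conclusion.** The point holds in a limited form. As written, SAP 3.5 excludes from all four TEAE tables, and from the serious, drug-reaction and discontinuation listings, an AE that starts before the first dose, keeps its onset date and then worsens on VAL201. The effect is on reported AE incidence, severity and causality, not directly on the MTD rule.

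The conclusion assumes that at least some worsenings are held as an update to the existing record, which the SAP leaves open. The documents give no rate of AEs starting between screening and first dose, nor of their worsening. A shortfall in percentage points therefore cannot be estimated; a prevalence of baseline symptoms would be the wrong input, because most such symptoms fall outside the affected window. What can be said is that, at these cohort sizes, one case moves a reported incidence from 100% or 33% to zero. The change should be made: it is cheap, and the study's purpose is safety.

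**What to change.** In SAP 3.5, define a TEAE as an AE that either starts at or after the first VAL201 administration, or starts before it and increases in CTCAE grade or becomes serious at or after it. For the second kind, use the post-dose grade and relationship in the tables. Use the date and time of first VAL201 administration as the single anchor for both classes. Apply the definition to all TEAE tables and listings.

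If the protocol or CRF instructions already require a worsening to be entered as a new AE with its own onset date, it would be enough to say so in 3.5 and to check before lock that sites did it.

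The cost is one clause and one derivation. If the AE form holds only one grade per event, the few pre-treatment AEs still ongoing at first dose need a review before database lock. AE counts may rise slightly.

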4.1 General

Results for dose-escalation phase will be listed and summarized using descriptive statistics. An exact 95% CI will be calculated for the response rate observed in dose escalation phase.

Descriptive summaries of continuous variables in terms of observed values will be provided. These summaries will contain arithmetic mean, SD, minimum, median and maximum or geometric mean and %CV in place of the arithmetic mean and SD for data requiring log transform due to known skewness (e.g. PSA).

Descriptive summaries of categorical variables will consist of frequencies and percentages.

All statistical analysis (i.e.: both efficacy and safety) will be done according to the actual treatment received due to the protocol's flexibility in allowing the cohort review committee to adjust the dose of individual patients. The most frequent dose taken by a subject during all treatment occasions in each cycle will be used for subject assignment to each treatment (dose) group for the purpose of the analysis; this is to cover any dosing subjects may have received by mistake occasionally only.

Any unscheduled visits will not be used for summary tables, but listed only.

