3.1 General design and plan

This clinical study is designed to establish the MTD/MAD, safety, tolerability and PK of VAL201 by testing the drug (VAL201) on patients with incurable, locally advanced or metastatic prostate cancer and other advanced solid tumors. The design is a Phase I/II, open-label single-arm dose escalation study. The study design consists of a dose escalation part followed by an enrichment part. The study features includes: five cohorts of up to six patients, six cycles (main study) each cycle will last 21 days and an extended treatment period of VAL201 if a patient is considered suitable. Events that occur during each cycle will be considered for Dose Limiting Toxicity (DLT) assessment and therefore to establish the MTD/MAD.

The dose escalation will follow an accelerated enrolment of 3+3 design where the first two cohorts will enroll 1 patient each with an accelerated dose escalation schedule as described on Section 4.2 of the clinical study protocol (VAL201-001 version F6.0). Each patient will be followed up for AEs and DLT during each cycle. Where the Cohort Review Committee (CRC) suspects that drug-related events have occurred that merit further exploration at that dose level, they will request that the cohort 1 or 2 must enroll 3 more patients in order to thoroughly evaluate safety events prior to escalation. Cohorts of 3 patients will be enrolled from the 3rd cohort onwards (or earlier where the CRC recommend due to safety data evaluation). After a DLT has been identified the cohort will be expanded to 6 patients. If a second DLT is reported this will be declared the MTD.

The starting dose of VAL201 for the first cohort of patients will be 0.5 mg/kg/dose given on Days 1, 8 and 15 of each cycle. In the absence of DLT, the dose of VAL201 will be escalated for future cohorts in recommended increments according to the rules for dose escalation as described in Section 4.2 of clinical study protocol. All dose escalation decisions will be made by a CRC who shall convene to review all available safety data.

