Intra-patient dose escalation will be adopted in Cohort 5; the CRC will evaluate the safety, clinical observations and PK data following cycle 1 (dosed at 8mg/kg) and approve escalation to 16 mg/kg on Cycle 4 Day 1. Based on the review of the safety data, the CRC may suggest an alternative dose regimen for the patient if required, to a maximum of 16 mg/kg. If a DLT occurs at 8 mg/kg requiring dose de-escalation, subsequent doses may be reduced. If a DLT occurs at 16 mg/kg, subsequent doses may also be reduced.

Cohort 6 will enroll a further 3 patients at a dose of up to 16 mg/kg; the dose will be decided upon by the CRC guided by safety, PK and PD data available from Cohort 5.

Once the MTD/MAD has been established for a given dose and schedule, up to 12 additional patients with incurable, locally advanced prostate cancer or other advanced solid tumors may be enrolled at this dose level (termed as “Enrichment Cohort”).

Thirty evaluable patients will be enrolled for the dose escalation part of the study and no more than 12 patients for the enrichment part of the study at the defined MTD/MAD for a total of 42 patients.

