3.2 Visit Schedule and Visit Windows

The study design for the starting dose of VAL201 includes the following visit schedule and visit windows:

 cros nt	Forms			
	Title	Statistical Analysis Plan Template		
	Code	Version	Effective Date	Page
	FRM_ST03_032	01	23 Apr 2015	9 of 24

Window	Description	Visit window	
		Min (day)	Max (day)
Screening	Within 28 days of enrollment to Cycle 1 Day 1	-28	0
Cycle 1	Visits scheduled at Day 1, Day 2, Day 8, Day 9, Day 15	1	1
Cycle 2 - 5	Visits scheduled at Day 1 (Day 22 of the previous Cycle), Day 8, Day 15	1	1
Cycle 6	Visits scheduled at Day 1 (Day 22 of Cycle 5), Day 8, Day 15	1	1
Final Cycle Visit	This visit is performed one week after the final dose of VAL201 in any cycle	1	1
Final Study Visit	This visit is performed 30 days after the final dose of VAL201 in any cycle	5	5

Where the CRC recommend an adjustment to the dose schedule, the following visit schedule and visit windows will be performed:

Window	Description	Visit window	
		Min (day)	Max (day)
Screening	Within 28 days of enrollment to Cycle 1 Day 1		
Cycle 1	Visits scheduled at Day 1, Day 2, Day 8, Day 15	1	1
Cycle 2 - 5	Visits scheduled at Day 1 (Day 22 of the previous Cycle), Day 8, Day 15	1	1
Cycle 6	Visits scheduled at Day 1 (Day 22 of Cycle 5), Day 8, Day 15	1	1
Final Cycle Visit	This visit is performed one week after the final dose of VAL201 in any cycle	1	1
Final Study Visit	This visit is performed 30 days after the final dose of VAL201 in any cycle	5	5

Where a patient continues to receive VAL201 after completion of main study, the following visit schedule and visit windows will be performed:

Window	Description	Visit window	
		Min (day)	Max (day)
Cycle 7 onwards	Visits scheduled at Day 1 (Day 22 of Cycle 6), Day 8, Day 15	1	1
Final Study Visit	This visit is performed 30 days after the final dose of VAL201 in any cycle	5	5

Forms				
Title		Statistical Analysis Plan Template		
Code		Version	Effective Date	Page
FRM_ST03_032		01	23 Apr 2015	10 of 24

The activities that will be performed at each cycle and day are summarized in the protocol under SCHEDULE OF STUDY ASSESSMENTS (table i, table ii and table iii).

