3.4.1 Secondary objective assessment

- Evaluation of AEs during treatment and follow up.
- Assessment of pharmacokinetics measures.
- Tumor assessments following PCWG2 and RECIST 1.1 recommendations and may include the following as appropriate:
 - assessment of measurable and any selected non-measurable lesions by MRI scan (or CT if not possible) of chest, and abdomen/pelvis at Screening and on the completion of every 2 cycles (every 3 cycles in Cohorts 5 and 6);

Forms			
Title		Statistical Analysis Plan Template	
Code		Version	Effective Date
FRM_ST03_032		01	23 Apr 2015
		11 of 24	

- assessment of PSA levels in serum at screening and every 3 weeks (or at the end of each cycle);
- assessment of bone lesions by a whole-body radionuclide scan at Screening and on the completion of every 2-4 cycles (3 cycles in Cohorts 5 and 6);
- other assessments e.g. whole body MRI may be assessed as requested by investigator.
- percent change in PSA from baseline to tumour assessment time point;

$$\text{Percent change} = [1 - \exp(\ln(\text{PSA}_{\text{C}}/\text{PSA}_{\text{B}}))] * 100;$$

where:

PSAb is the PSA at the screening (day -28 to 0)

PSA_C is the PSA at day 1 of each cycle (x indicates the cycle 1 to 7 and onwards)

- maximum decline in PSA during study defined as the maximum reduction in PSA from the baseline (looking at all visits, following Cycle 1 Day 1, which is indeed Baseline Visit for PSA, up to the last final cycle visit or the last dosing visit, if final cycle visit is not present, inclusive); this value will be determined by the percent change in PSA from baseline, a negative percent will indicate a decline in PSA.
- based on the three pre-treatment PSA values, an estimate of pre-treatment PSA doubling time will be derived by regressing the natural log of the PSA values versus the time points, the slope of the regression will be used to estimate pre-treatment PSA doubling time

$$\ln(\text{PSA}) = a + bt_x$$

$$\text{doubling time: } \ln(2)/b$$

where \ln is the natural logarithm

a is the intercept,

b is the slope,

t_x are the time where the PSA test was performed.

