5.12 Tumour assessment prostate

Tumour assessment for prostate cancer patients will follow the PCWG2 guidelines or RECIST 1.1 guidelines and may include assessment of serum prostate-specific antigen (PSA) at screening and every 3 weeks or at the end of every cycle.

Forms				
Title		Statistical Analysis Plan Template		
Code		Version	Effective Date	Page
FRM_ST03_032		01	23 Apr 2015	19 of 24

A summary table for tumour assessment at screening and at each applicable cycle will be produced presenting descriptive statistics for longest tumour diameter (mm) reported as well as duration of tumour (years) and method of examination; longest tumour diameter will be classified by tumour location and such categories will be defined by a study medical expert reviewing the related information collected.

The assessment of prostate-specific antigen PSA outcomes will be summarised for each patient and time point including the percent change in PSA from baseline to tumour assessment time point.

An estimate of pre-treatment PSA doubling time will be presented in a summary table together with descriptive statistics for PSA values at each cycle and the related percent change from baseline.

Baseline PSA value is defined as the last available assessment before treatment start (which will be actually the PSA value collected at Cycle 1 Day 1).

Thereafter tumour assessment and prostate-specific antigen PSA assessment results will be listed, including also maximum decline in PSA during study.

If other methods were used to assess the tumour such CT scan or MRI then the results of the tests will be listed for each patient by time point.

6. Evaluation of objectives

The evaluation of the primary objective will be based on the safety set, the evaluation of the secondary objective will be based on the ITT set and the evaluation of the exploratory objective will be based on the ITT set and the PP set separately. Tables and listings will be presented separately.

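### Section 4.1 gives a Day 1 value the dose of the cycle it opens, so an escalated Cohort 5 patient's Cycle 4 Day 1 PSA counts as 16 mg/kg before any 16 mg/kg dose has acted

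*SAP*

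**What the plan says.** **Dose group.** SAP section 4.1 states: "All statistical analysis (i.e.: both efficacy and safety) will be done according to the actual treatment received". It then gives the working rule: "The most frequent dose taken by a subject during all treatment occasions in each cycle will be used for subject assignment". Nothing in 4.1 links a measurement taken at the start of a cycle to the dose of the cycle before.

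**PSA time point.** In section 3.4.1 the post-baseline term of the percent-change formula "is the PSA at day 1 of each cycle (x indicates the cycle 1 to 7 and onwards").

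**What Day 1 is.** For Cycles 2 to 5, section 3.2 has: "Visits scheduled at Day 1 (Day 22 of the previous Cycle), Day 8, Day 15". Day 1 therefore also closes the previous cycle. Section 5.12 defines the PSA baseline as the "last available assessment before treatment start (which will be actually the PSA value collected at Cycle 1 Day 1"), so at Cycle 1 the Day 1 sample precedes dosing.

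**Dose change in Cohort 5.** Section 3.1 has the Cohort Review Committee (CRC) review data "following cycle 1 (dosed at 8mg/kg) and approve escalation to 16 mg/kg on Cycle 4 Day 1". Section 4.6 words the change as a possibility, not a certainty.

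**Other measurements.** Section 4.6 places testosterone, LH and PSA within clinical chemistry, which section 5.11 schedules on Days 1, 8 and 15. Sections 5.7 and 5.9 state that Day 1 ECOG (Cycles 2 to 6) and dosing-day vital signs precede the dose.

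**The concern.** The same-cycle rule suits anything that arises after dosing within a cycle, such as an adverse event. It does not suit a value taken before the first dose of that cycle, because that value can only reflect earlier doses. While the dose stays constant the two labels agree and nothing is lost. When the dose changes between cycles, the first value after the change gets the new label although it was reached wholly on the old dose.

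Cohort 5 is where this is planned to happen, and it is the one cohort with planned within-patient escalation. A by-dose display of PSA or hormones would put a value reached on 8 mg/kg in the 16 mg/kg group. With small cohorts and purely descriptive summaries, one misplaced value per patient can visibly change what a reader takes from a cell.

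**Working it through.** The SAP gives no figure of its own on this point, so the check is a count along the dosing calendar of a Cohort 5 patient who is escalated as planned.

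**Inputs**
- Cycle length 21 days, six cycles in the main study (section 3.1).
- Doses "given on Days 1, 8 and 15 of each cycle" (section 3.1), so three per cycle.
- 8 mg/kg in Cycles 1 to 3 and 16 mg/kg in Cycles 4 to 6 (section 3.1, assuming the escalation takes place).
- Day 1 samples taken before that day's dose (implied by section 5.12 for Cycle 1 PSA; assumed for later laboratory samples).

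**Formulas.** Study day of Cycle c Day 1 = 21 × (c − 1) + 1. Doses received before it = 3 × (c − 1).

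| Visit | Study day | Prior doses at 8 mg/kg | Prior doses at 16 mg/kg | Label under 4.1 | Label from preceding cycle |
|---|---|---|---|---|---|
| Cycle 1 Day 1 | 1 | 0 | 0 | 8 | none (baseline) |
| Cycle 2 Day 1 | 22 | 3 | 0 | 8 | 8 |
| Cycle 3 Day 1 | 43 | 6 | 0 | 8 | 8 |
| Cycle 4 Day 1 | 64 | 9 | 0 | **16** | **8** |
| Cycle 5 Day 1 | 85 | 9 | 3 | 16 | 16 |
| Cycle 6 Day 1 | 106 | 9 | 6 | 16 | 16 |
| Cycle 6 Day 22/Cycle 7 Day 1 | 127 | 9 | 9 | depends on which cycle it is counted in | 16 |

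At Cycle 4 Day 1 the last dose was 8 mg/kg on Cycle 3 Day 15, study day 21 × 2 + 15 = 57, which is 64 − 57 = 7 days earlier. All three Cycle 4 doses are 16 mg/kg, so the rule in 4.1 returns 16 mg/kg.

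**Size by type of measurement, Cycles 4 to 6**
- PSA as defined in 3.4.1: three Day 1 values, of which one is mislabelled (1 of 3).
- Day 1 ECOG: also 1 of 3, with no assumption about timing.
- LH and testosterone: 3 days × 3 cycles = 9 scheduled values, of which one is mislabelled (1 of 9). Cycle 4 Days 8 and 15 follow one and two doses of 16 mg/kg respectively.

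Moving to the preceding cycle's dose changes one post-baseline main-study visit, Cycle 4 Day 1. Cycles 2, 3, 5 and 6 keep their label.

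**The case against.** Several points on the other side have weight.

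- **The by-dose layout of PSA is inferred.** In section 7.2.1 only adverse event tables carry dose in their titles, while DLTs are by cohort. The PSA titles name no dose split, and the chemistry tables are organised by cycle and time point. Section 5.11 mentions dose group for listings, and section 5.12 summarises PSA by patient and time point. The table shells are in an appendix that is not at hand. This stands as a limit on reach. It does not remove the point, because 4.1 applies the rule to every analysis.
- **Pre-dose laboratory sampling is not stated after Cycle 1.** That is true. Even if the sample followed the dose, it would reflect one dose of 16 mg/kg against nine of 8 mg/kg.
- **Escalation was conditional.** Only patients actually escalated are affected, and the SAP gives no count of them.
- **No formal dose-response analysis is planned.** The MTD/MAD rests on DLTs, and the responder definition in 4.5 rests on progression over six cycles. Neither uses the dose label of a Day 1 value. This stands in full.

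Three stronger readings are tempting but not supported. A reader might infer that the whole dose-response series is displaced by a cycle; the calendar shows a single visit moving. A reader might infer that hormones are observed only on Day 1; section 5.11 also samples them on Days 8 and 15. A reader might infer that the outcome after Cycle 6 has no dose group. Section 4.6, however, names that visit as Cycle 6 Day 22 as well as Cycle 7 Day 1 and puts it in the main-study tables, so it can fairly be read as a Cycle 6 value with the Cycle 6 dose. The wording could be clearer, but a gap is not shown.

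**Conclusion.** The point holds in a limited form. As written, 4.1 places the pre-dose Cycle 4 Day 1 value of an escalated Cohort 5 patient under 16 mg/kg after nine doses of 8 mg/kg and none of 16 mg/kg. The same would happen to any other patient whose dose changes between cycles.

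The effect is one Day 1 visit per dose change. It matters only where results are shown by dose group, and it leaves the MTD/MAD and response rate unchanged. The conclusion assumes that the escalation took place at Cycle 4 Day 1 and, for laboratory values, that Day 1 samples precede dosing. It concerns how values are labelled in the analysis and says nothing about which dose should be given.

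**What to change.** Add to section 4.1:
- Values taken before dosing on Day 1 of Cycle 2 or later (PSA, LH, testosterone, other Day 1 laboratory values, ECOG, pre-dose vital signs) are assigned to the most frequent dose of the preceding cycle.
- Cycle 1 Day 1 is baseline, as section 5.12 already has it for PSA.
- For clarity, values at Cycle 6 Day 22/Cycle 7 Day 1 take the Cycle 6 dose.

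Day 8 and Day 15 values, post-dose Day 1 readings and adverse events that start after dosing keep the same-cycle rule. A short statement in 5.11 that Day 1 laboratory samples precede dosing, if that is the case, would remove the remaining assumption.

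The cost is a few lines of SAP text and a one-cycle lag in the dose-group derivation for these values. No new data or additional analyses are needed.
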